6 STUDY POPULATION AND SELECTION OF PATIENTS

6.1 SAMPLE SIZE AND STUDY TIMETABLE, FOR THE COHORT STUDY

It is planned to recruit 325 pregnant women. Recruitment goals are set at 75 in the exposed group (Cohort I), and 125 in each of the other 2 comparison groups (Cohorts II and III). The sample size target was selected as realistic based on experience with recruitment in previous pregnancy registries, and the expectation that with effective labeling medication guidance, few pregnancies will occur with inadvertent exposure to teriflunomide, as has been the case with leflunomide. Given the limitations of the sample size in teriflunomide-exposed, a somewhat larger target sample size was selected for the 2 comparison groups to improve statistical power, as the pool of available subjects meeting the inclusion criteria for these 2 groups is much larger.

Study enrollment will be for 5 years. Enrollment will begin in Canada once teriflunomide is approved by local authorities.

6.2 ELIGIBILITY CRITERIA

Eligibility for the study includes the following:

- Residence in the U.S. or Canada at the time of enrollment
- Currently pregnant woman

6.2.1 Inclusion criteria for the cohort study

Cohort I: Teriflunomide-exposed pregnant women with MS

- Pregnant women who have previously been treated with teriflunomide, including women who were treated during a clinical trial, who are participating in another registry, or who are treated with other approved disease modifying therapy for MS, for any number of days, at any dose, and at anytime from the 1st day of the last menstrual period up to and including the 12th week after the first day of the LMP.
- Pregnant women who have provided an oral and/or written consent to enroll no later than 20 completed weeks from LMP.
- Pregnant women who agree to the conditions and requirements of the study including the interview schedule, release of medical records, and the physical examination of live born infants (up to 1 year post birth).

Cohort II – Pregnant women with MS not exposed to teriflunomide during the current pregnancy

- Pregnant women with a diagnosis of MS who have:
 1. Not taken teriflunomide at any time but who may or may not have taken another medication for MS during the current pregnancy, **or**
 2. Previously been treated with teriflunomide within 2 years prior to the index pregnancy and have documented blood levels below 0.02 mcg/mL prior to pregnancy, **or**
 3. Previously been treated with teriflunomide greater than 2 years prior to the index pregnancy
- Pregnant women who have provided oral and/or written consent to enroll no later than 20 completed weeks from LMP.
- Pregnant women who agree to the conditions and requirements of the study including the interview schedule, release of medical records, and the physical examination of live born infants (up to 1 year post birth)
- Pregnant women can be taking any other approved disease modifying therapy for MS

Cohort III - Pregnant women without MS and no exposure to any known human teratogen

- Pregnant women who do not have a known diagnosis of MS and have no known exposure to a known human teratogen, as determined by the referring Teratogen Information Specialists and confirmed by the OTIS Research Center.
- Pregnant women who have provided oral and/or written consent to enroll no later than 20 completed weeks from LMP.
- Pregnant women who agree to the conditions and requirements of the study including the interview schedule, release of medical records, and the physical examination of live born infants (up to 1 year post birth).

6.2.2 Exclusion criteria for Cohort Study

Cohort I: Teriflunomide-exposed pregnant women with MS

- Pregnant women with exposure to teriflunomide commencing after the 12th week post-LMP.
- Pregnant women who come in first contact with the project after prenatal diagnosis of a major structural defect.
- Pregnant women who first come in contact with the project after 20 completed weeks' gestation.

- Pregnant women who had previously enrolled in the study for a previous pregnancy (only 1 pregnancy, per woman, may be registered).
- Retrospectively reported cases.

Cohort II: Pregnant women with MS not exposed to teriflunomide during the current pregnancy

- Pregnant women who come in first contact with the project after prenatal diagnosis of a major structural defect.
- Pregnant women who first come in contact with the project after 20 completed weeks' gestation.
- Pregnant women who had previously enrolled in the study for a previous pregnancy (only 1 pregnancy, per woman, may be registered).
- Retrospectively reported cases.
- Pregnant women who had previously been treated with teriflunomide if they had received any dose of the drug within 2 years prior to the index pregnancy and do not have documented blood levels below 0.02 mcg/mL prior to pregnancy.

Cohort III: Pregnant women without MS and no exposure to any known human teratogen

- Pregnant women who first come in contact with the project after 20 completed weeks' gestation.
- Pregnant women who first come in contact with the project after prenatal diagnosis of a major structural defect.
- Pregnant women who had previously enrolled in the study for a previous pregnancy (only 1 pregnancy, per woman, may be registered).
- Retrospectively reported cases.

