3.2.1 Cohort study potential biases, limitations and strengths

The primary limitation of a cohort study utilizing volunteer subjects is selection bias (Honein et al, 1999)(4). The use of comparably selected controls in both groups will address this concern to some extent. However, women who agree to enroll in the cohort study may represent particularly high or low risk pregnancies. However, the study results will be strictly generalizable to women fitting the profile of the sample of pregnant women who enroll.

Because early prenatal testing is prevalent in the US and Canada, it may be difficult to achieve adequate numbers of patients, if all pregnancies with prior prenatal testing were excluded from the analysis. Therefore, the registry cohort study will include pregnancies, enrolled prior to outcome, but after a prenatal test, as long as the test does not indicate a fetus with a major structural defect. The FDA guidance document, "Guidance for Industry, Establishing Pregnancy Exposure Registries" dated August, 2002(5) acknowledges that such an approach may be necessary to accrue adequate numbers. However, this practice could potentially bias the results by lowering the overall birth prevalence of birth defects among

those with normal prenatal test results. The data analysis will address this by stratifying use of prenatal testing prior to enrollment.

The calculation of frequency of birth defects excludes fetal losses (spontaneous abortions, induced abortions, or fetal deaths) for which no birth defects have been detected as they may introduce a classification bias. It is unknown what percentage of these pregnancies consists of potentially normal outcomes or birth defects. The registry study attempts to obtain information on birth defects detected at the time of the outcome. However, the malformation status of the aborted fetus may not be known.

It is expected that virtually all exposures to teriflunomide will occur in unintended pregnancies. More than half of all pregnancies in the U.S. are unintended, (Henshaw, 1998)(6) and this may lead to age, race, and other biases in the sample. For example, the rate of unintended pregnancies is higher among low-income women/families than among the other socioeconomic groups (Finer & Zolner, 2011)(7). Data on intendedness of pregnancy is collected as part of the study interview from all mothers. These factors will be taken into consideration in the recruitment of comparison groups and in the analysis.

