6.3 MODALITIES OF RECRUITMENT

All exposed subjects and comparison subjects will be recruited through spontaneous calls to participating OTIS member services locations throughout North America, and through active recruitment strategies, e.g., direct mailings to neurologists, obstetricians, web site, Clinicaltrials.gov website, professional meetings, and the Sponsor's Call Center. Each OTIS service representative will provide exposure counseling, in the routine manner, for all exposed and unexposed women, who initially make contact with the service with questions regarding a current pregnancy. Subsequently, each OTIS service representative will explain the study protocol to potentially eligible participants, and then will request permission to refer the woman to the registry study, enrolling at the University of California, San Diego. Potential subjects who agree to be referred will be contacted by the OTIS registry study staff or will be

CSD-003149 VERSION N°1.0 (20-JUL-2010)

Ensure that the printed copy of this document is the current version available on the Intranet.

given information to initiate contact themselves if they prefer. OTIS member services will also refer callers, to the registry study, for those women whose exposure to teriflunomide does not appear to qualify for the cohort study (e.g., first contact after 20 completed weeks gestation, repeat pregnancies, or retrospective reports), as these will be handled as Registry Case Reports (See [Section 10.3](#)).

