7.3 PROCEDURE FOR WITHDRAWAL OF PATIENTS FROM STUDY FOLLOW-UP SCHEDULE

Participants, who meet the study criteria, consent to participation, and complete the intake interview will be considered enrolled. Every effort will be made by the OTIS Research Center Staff to complete all study visits as scheduled, and to collect outcome interview, medical records, and physical examination data. Subjects who do not complete the outcome interview following the end of the pregnancy will be considered lost to follow-up. Multiple attempts will be made to contact participants by telephone, mail, email, up to 1 year past the expected due date before a subject is deemed lost. Subjects who decline to complete participation after enrollment will be considered to have withdrawn consent and information collected on reasons for withdrawal. The statistical analysis plan will specify how these patients for whom outcome information is not available for study endpoints will be considered.

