10.4 MONITORING METHODS FOR REGISTRY CASE REPORTS

The intent of the registry study is to determine whether there is a signal that might indicate a potential risk of major birth defects in the offspring of pregnant women following an exposure to teriflunomide during pregnancy. The major strength of the registry study is that the data is collected in the prospective cohort study, before there is a known outcome of the pregnancy. For this reason there is no potential for bias in ascertainment based on known outcome. In addition, the prospective cohort study involves comparison to 2 control groups (disease-matched and healthy) that are internally and contemporaneously generated and provide more appropriate comparisons than general population statistics. Furthermore, the prospective study includes a level of outcome evaluation with a dysmorphological examination that exceeds that of any other method.

Registry study case reports, outside the cohort, can be used to illuminate knowledge gained from the cohort study, for example, to determine if an unusual pattern of malformation identified in the cohort study is or is not also noted in any infants in the case report series. Therefore, the OTIS Scientific Advisory Committee and the investigators will consider the

Registry study case reports when reviewing the cohort study data for the appearance of any unusual events, problem cases, or unexpected numbers of specific events. All reports of major birth defects are transmitted promptly to the sponsor to meet regulatory reporting.

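### The prenatal-diagnosis exclusion runs from a loosely defined first contact in 6.2.2 but from enrolment in 3.2.1, so the status of a woman diagnosed between first call and consent is contradictory

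*Protocol*

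**What the plan says.** For Cohorts I and II, Protocol 6.2.2 excludes "Pregnant women who come in first contact with the project after prenatal diagnosis of a major structural defect". For Cohort III it excludes "Pregnant women who first come in contact with the project after prenatal diagnosis of a major structural defect". The synopsis repeats these rules. All three are anchored to first contact.

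Joining the cohort takes several steps. Under 6.3 a caller is counselled by an OTIS member service, which "then will request permission to refer the woman to the registry study, enrolling at the University of California, San Diego". A woman who agrees is called by registry staff or "given information to initiate contact themselves if they prefer". Under 6.3.2 the Research Center screens her and takes oral consent before the first interview. Section 6.2.1 allows "consent to enroll no later than 20 completed weeks from LMP". Section 7.3 fixes the end point: "Participants, who meet the study criteria, consent to participation, and complete the intake interview will be considered enrolled".

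Section 3.2.1 states the rule differently. It admits any pregnancy "enrolled prior to outcome, but after a prenatal test, as long as the test does not indicate a fetus with a major structural defect". Here enrolment is the anchor.

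Section 10.3 lists the exposed pregnancies that become case reports. It again uses first contact, but with the Study Center rather than the project. Section 10.3.2 gives as an example women who already have a prenatal diagnosis of a major defect, with no first-contact qualifier, and keeps them out of the primary analysis.

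Section 10.4 says that data in the prospective cohort are collected before the outcome is known, and concludes: "For this reason there is no potential for bias in ascertainment based on known outcome".

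**The concern.** The defect is the primary endpoint. If a woman can learn of it and then decide whether to join, entry into the primary numerator may depend on the outcome. That is the selection a prospective registry is meant to prevent, and 10.4 says it cannot occur here.

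The protocol recognises that contact and consent differ. For the 20-week limit it sets both a consent rule (6.2.1) and a first-contact rule (6.2.2). For a known defect, the eligibility lists set only the first-contact rule.

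Few events are expected, so a handful of doubtful admissions could change the estimate noticeably. Staff who screen from 6.2.2 and staff who follow 3.2.1 could classify the same woman differently.

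**Working it through.** **Step 1: the sections side by side.** Take two hypothetical women, each diagnosed at 18 weeks and consenting at 19 weeks. Both are within the 20-week consent limit. The weeks are illustrative.

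- *Woman A* calls an OTIS member service at 8 weeks and first reaches registry staff at 19 weeks.
- *Woman B* reaches the Research Center at 8 weeks but does not consent until 19 weeks.

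| Section | Anchor | Woman A | Woman B |
|---|---|---|---|
| 6.2.2 and synopsis | First contact with the project | Not excluded if a member service counts as the project; excluded if only the Study Center counts | Not excluded on either reading |
| 3.2.1 | Enrolment | Not included | Not included |
| 10.3 | First contact with the Study Center | Case report | Not caught |
| 10.3.2 | Diagnosis already made, no first-contact qualifier | Case report | Arguable, because the example illustrates women who fail the cohort criteria, which leads back to 6.2.2 |

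Section 6.3 supports the wider reading of contact, since it has member services recognise callers whose first contact is after 20 completed weeks. Section 10.3 supports the narrower one. The exclusion of retrospectively reported cases does not clearly close the gap: the term is not defined, and 6.2.2 and 10.3 list it separately from prenatal diagnosis.

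**Step 2: the plan's own figure.** Section 8.4 and Table 3 give 64 and 106 live births (75 × 0.85 = 63.75; 125 × 0.85 = 106.25), a 3% comparison rate and a detectable relative risk of 5.57. The exposed rate is then 0.03 × 5.57 = 16.71%. Exact power of Fisher's test is 80.9% with 0.025 in the direction of harm. It is 84.5% with the usual two-sided exact p-value, which reaches 80% at a relative risk of about 5.23. The stated figure is reproduced and is not in dispute.

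**Step 3: sensitivity to a few entrants (assumption).** Assume no true effect, 3% in both cohorts, and k live births with an already known defect among the 64 exposed, with none in Cohort II. The protocol does not give k.

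Expected defects with k = 0: 64 × 0.03 = 1.92 and 106 × 0.03 = 3.18, about 5.1 in total.

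Expected exposed rate = ((64 − k) × 0.03 + k) / 64. Relative risk = that rate / 0.03.

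| k | Expected exposed defects | Exposed rate | Relative risk | Chance of a significant Fisher result towards harm |
|---|---|---|---|---|
| 0 | 1.92 | 3.0% | 1.0 | 1.2% |
| 1 | 1.89 + 1 = 2.89 | 4.5% | 1.5 | 3.2% |
| 2 | 1.86 + 2 = 3.86 | 6.0% | 2.0 | 7.7% |
| 3 | 1.83 + 3 = 4.83 | 7.5% | 2.5 | 15.6% |

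The last column is by exact enumeration with two-sided p ≤ 0.05. One entrant moves the point estimate visibly but rarely changes the test result.

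**The case against.** The strongest reply is that the protocol already keeps these women out. Section 3.2.1 admits a post-test pregnancy only if the test shows no major defect, 10.3 uses the Study Center as the contact point, and 10.3.2 directs women with an existing diagnosis to the case reports. If contact means the Research Center, the same staff screen and take oral consent, so the window may be short. This stands as evidence of intent. It does not settle the rule, because the list used for screening says something else and Woman B passes it on either reading.

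Second, the numbers are probably small. Section 8.4 expects enrolment at an average of 6 to 9 weeks, which leaves little time for a diagnosis first. The primary endpoint counts live births only, so a gap case ending in termination affects only the secondary analysis of all pregnancies. Both points stand, and they limit how serious this is.

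Third, the criterion is the same in every cohort. A reader might infer that exposed women with an affected fetus would be keener to join, so that the bias runs towards harm. The protocol contains nothing on this, so the direction is unknown.

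Fourth, 3.2.1 and 8.3.1 plan to stratify by prenatal testing or diagnosis before enrolment. Prenatal test results, gestational age at enrolment and a screening log are also recorded (7.2, 7.2.2, 7.2.3, 8.2). These would help to identify such cases but would not exclude them, and about five expected events cannot support much stratification.

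Fifth, moving the anchor to completion of the intake interview would remove women who had already consented, because of their outcome. That is a fair criticism of an intake anchor and a reason to use oral consent.

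**Conclusion.** The point holds as an internal contradiction with an undefined anchor. Sections 6.2.2, 3.2.1, 10.3 and 10.3.2 do not give one answer for a woman diagnosed between first contact and consent. Followed literally, 6.2.2 lets her into the cohort with the primary outcome known, contrary to 3.2.1 and to the assurance in 10.4.

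A reader might go further and conclude that the protocol plainly admits such women, or that the primary comparison is biased towards harm. The text supports neither: 3.2.1 bars them, 10.3.2 points them to the case series, and nothing is said about how many there would be or in which cohort.

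The relative risks of about 1.5 and 2.0 for one and two entrants rest on three assumptions: entry in the exposed cohort only, no true effect, and the planned 64 and 106 live births at 3%. They show how sensitive about five expected events are to a single case; they do not predict what will happen. The effect is probably small, but the rule decides who enters the primary numerator and costs little to settle.

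**What to change.** In the synopsis and 6.2.2, for all three cohorts, exclude any woman whose fetus was diagnosed prenatally with a major structural defect before she gave oral consent to enrol. Oral consent is the decision to join, so no woman who has already consented is removed because of her outcome.

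Align 10.3 and 10.3.2 so that teriflunomide-exposed women diagnosed between first contact and consent go to the Registry Case Report series. Reword 3.2.1 to the same anchor, since 7.3 places enrolment slightly later, at the intake interview. Define first contact once, saying whether a call to a member service counts, and use one term throughout. Record the dates of first contact, oral consent and intake interview for every woman.

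The cost is a few sentences and three dates per woman. A few exposed women may move from the cohort to the case series, where their data are kept; comparison women in the same position would simply be excluded. The bias that 3.2.1 already acknowledges, a lower defect prevalence among women enrolled after a normal prenatal test, remains and is still addressed by the planned stratification.

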6.3 MODALITIES OF RECRUITMENT

All exposed subjects and comparison subjects will be recruited through spontaneous calls to participating OTIS member services locations throughout North America, and through active recruitment strategies, e.g., direct mailings to neurologists, obstetricians, web site, Clinicaltrials.gov website, professional meetings, and the Sponsor's Call Center. Each OTIS service representative will provide exposure counseling, in the routine manner, for all exposed and unexposed women, who initially make contact with the service with questions regarding a current pregnancy. Subsequently, each OTIS service representative will explain the study protocol to potentially eligible participants, and then will request permission to refer the woman to the registry study, enrolling at the University of California, San Diego. Potential subjects who agree to be referred will be contacted by the OTIS registry study staff or will be

CSD-003149 VERSION N°1.0 (20-JUL-2010)

Ensure that the printed copy of this document is the current version available on the Intranet.

given information to initiate contact themselves if they prefer. OTIS member services will also refer callers, to the registry study, for those women whose exposure to teriflunomide does not appear to qualify for the cohort study (e.g., first contact after 20 completed weeks gestation, repeat pregnancies, or retrospective reports), as these will be handled as Registry Case Reports (See [Section 10.3](#)).

6.3.1 Investigator selection

The Principal Investigator and Co-Investigators for this study were selected for their expertise in teratology, experience in conducting pregnancy outcome research related to human teratogenicity, experience in leading collaborative research studies, including pregnancy registries, and experience specifically in designing and implementing pregnancy registry study designs that involve internal control groups.

6.3.2 Participant selection

Women who may meet the inclusion and exclusion criteria for the study are referred to the OTIS Research Center by OTIS referral sites, by clinician referral, by self-referral, or other sources such as the Sponsor's Call Center. Women are screened at the OTIS Research Center for inclusion and exclusion criteria. Women who meet the criteria and are interested in participating in the study are administered oral informed consent by trained OTIS Research Center staff, prior to the first maternal telephone interview. Subsequently, signed informed consent and Health Insurance Portability and Accountability Act (HIPAA) consent are obtained from all enrolled women either via mail, or in-person, at the time of the physical examination. Women who do or do not meet the criteria for enrollment following teriflunomide exposure will be offered referral information for laboratories where blood levels of teriflunomide can be measured and information about the drug elimination procedure will be provided.

The OTIS Research Center staff will be responsible for verifying the participant selection criteria, enrolling each participant and securing informed consent, oral and written, providing all pregnancy follow-up interviews and medical record review, scheduling dysmorphological examinations, recording and storage of all data, and subsequent data analysis.

